9.2 Pharmacodynamics

Tumor tissue: Evaluation of drug effect on DNA damage response will be performed by immunofluorescence assay for measurement of γ H2AX levels and other biomarkers of DNA damage response/repair. Epithelial-mesenchymal transition (EMT), MGMT, and levels of cCasp3 (apoptosis) will also be measured. Any remaining tumor tissue may be formalin-fixed and paraffin-embedded and sent to the laboratory of [name] (Case Western Reserve University) for IHC assessment of the enzyme N-methylpurine DNA glycosylase (MPG). No patient data will accompany any samples sent to [name] lab.

9.2.1 Laboratory Contact

At least 24 hours prior to tumor biopsy or blood sample collection, the research nurse will contact the NCI Phase I/II PK/PD Support Group in NIH Building 10:
E-mail (preferred): [contact]

Pager (preferred): [name]
[contact]
[contact].

For biopsies, tubes pre-labeled with the information specified in [Section 9.2.4](#), biopsy date, and site of tissue biopsy will be provided. Initial processing and shipping of the samples will be completed as described below. If a patient had a biopsy within the past 3 months and had no treatment since that biopsy, an attempt will be made to obtain and process that tissue as the baseline biopsy.

9.2.2 Blood Collection for CTC Studies (Optional)

At each time point, whole blood (at least 7.5 mL) will be collected aseptically by venipuncture or from a venous port into one 10 mL Streck tube (catalog number 218962). One 10 mL RareCyte tube (catalog number 24-1070-005) is also acceptable. Tubes must be inverted 8 times to ensure adequate mixing of the additive. Blood samples for CTCs will be collected from patients at the following time points:

Phase I

- Cycle 1 prior to treatment
- Cycle 1, day 1: 8 hrs after drug in both the escalation and expansion phases
- Cycle 1, day 5 (± 1 day in case of scheduling difficulties): before drug in the expansion phase only
- Cycle 2, day 1: before drug in both the escalation and expansion phases
- Day 1 of all subsequent cycles: before drug in both the escalation and expansion phases
- At time of disease progression

Phase II

- Cycle 1 prior to treatment
- Cycle 1 day 4 or 5 before drug (on the same day as the post-dose biopsy)
- Day 1 (± 1 day) of all subsequent cycles before drug
- At time of disease progression

Blood for CTC analysis will be shipped to the PADIS laboratory on the day it is collected. Arrangement will be made for pickup with the CSP courier service [contact]) and the receiving laboratory will be notified by email of the shipment ([contact]). Because of the 48-hour window of CTC sample stability, no CTC specimens should be collected or shipped on Friday afternoon.

Samples will be sent to:

Attn: PADIS CTC Laboratory
Frederick National Laboratory for Cancer Research
Leidos Biomedical Research, Inc.
[name]
[name]
[name]

[contact]
[contact]

9.2.2.1 Measurement of Circulating Tumor Cells (CTC) in Peripheral Blood

PADIS, Frederick National Lab, is developing and validating the process to isolate circulating tumor cells using the ApoStream™ technology platform which uses size and cell surface charge to isolate cancer cells; this platform is of particular interest in that it can detect CTCs from patients with cancer of mesenchymal origin, such as sarcomas.

9.2.3 Tumor Biopsies

9.2.3.1 Timing of tumor biopsies

Biopsies will be optional during the escalation phase and mandatory in up to 15 additional patients enrolled at the MTD during the Phase I expansion phase and during the Phase II portion of the study (patients with NSCLC will not be biopsied). Biopsies will be collected:

- before drug administration on study (baseline), and
- post-treatment:
 - Phase I: on cycle 1, day 5 (\pm 1 day in case of scheduling difficulties), 3-4 hrs after drug
 - Phase II: on cycle 1, day 4 or 5, 3-4 hrs after drug
- OPTIONAL—One optional tumor biopsy may be collected:
 - A restaging follow-up biopsy may be performed on day 1 (\pm 2 days) of the cycle following any restaging at which a 10-19% increase in tumor volume is observed (according to RECIST criteria) if the patient has been on study for at least 4 cycles

OR

- A progression tumor biopsy may be performed at the time of disease progression

9.2.3.2 Biopsy Procedure

Serial tumor biopsies will be obtained by the Interventional Radiology team by a percutaneous approach, a dermatologist for skin lesions, or an ENT for lesions that are easily biopsiable through ENT exam. If the patient has skin lesions or peripheral lymph nodes that are easily accessible by the dermatologist or surgeon and could be done under local anesthesia with < 5% risk of complications, this will be acceptable if agreeable with the patient and investigator. If considered feasible and safe by the biopsy team, up to five core biopsies \geq 18 gauge in diameter and \geq 1 cm in length, or equivalent, will be obtained during each procedure. It is estimated that there will be between 2 million–5 million cells from each biopsy. If a site is deemed appropriate for biopsy with minimal risk to the participant by agreement between the investigators and the biopsy team, an attempt for biopsy will be made. If possible, the lesion from which each biopsy is taken will be documented.

The use of imaging to facilitate biopsies will be decided by members of the biopsy team and may include ultrasound, CT scan, or MRI. Should a CT scan be needed for biopsy, the number of scans for each procedure will be limited to the minimum number needed to safely obtain a biopsy. Tumor biopsies and local anesthesia will be administered only if they are considered to be of low risk to the participant, as determined by the investigators and the biopsy team. In the expansion cohort, if the participant chooses not to undergo tumor biopsy after the initial attempt, he/she will still remain in the study and receive study medication, and all the other correlative studies will be performed.

Tumor biopsies are optional during the escalation phase but mandatory for the 15 additional patients enrolled at the MTD during the expansion phase and Phase II portion of the study. Baseline biopsies will be performed following patient enrolling on study or if the patient had a biopsy within the past 3 months and had no treatment since that biopsy, an attempt will be made to obtain and process that tissue as baseline biopsy. If the tissue could not be used for planned PD studies, a biopsy will be performed. If an initial attempt at biopsy is unsuccessful, the patient will be given an option to proceed with a repeated attempt. A separate consent form must be signed for each biopsy procedure, so patients may choose not to undergo subsequent biopsies. If the baseline biopsy is unsuccessful or the patient refuses to undergo subsequent biopsies, no further biopsies will be performed but the patient will remain on study, receive study medication, and other correlative studies will be performed. The patient will be replaced in the accrual scheme of the expansion phase.

9.2.3.3 Solid Tumor Biopsy Processing

Up to five tissue cores, or equivalent, will be collected and flash frozen in liquid nitrogen and submitted for evaluation of DNA damage markers, and H&E pathology evaluation. The frozen biopsy specimens are transferred to PADIS, where the biopsy samples are stored at -80°C until processing. Refer to SOP340507 (https://dctd.cancer.gov/ResearchResources/biomarkers/docs/par/SOP340507_Biopsy_Frozen.pdf) for detailed instructions on biopsy collection and handling. The sample shipping manifest and batch record are included in SOP340507. Biopsy samples will be analyzed for PD and genomic analyses based on the assay prioritization shown in [Figure 4](#) and the discretion of the PI.

Biopsies will be shipped on dry ice to:

ATTN: PADIS IQC Lab
Frederick National Laboratory for Cancer Research
Leidos Biomedical Research, Inc.
[name]
[name]
[name]
[contact] or [contact]
[contact]

Shipment should be by CSP Courier and may be arranged by contacting [name], FNLCR, [contact]

Note: Per the discretion of the PI, restaging follow-up or progression biopsies may be collected per SOP to be used for analyses other than those listed here, including analyses carried out as a part of other DTC clinical trials.

9.2.3.4 Archival Tissue Submission

Archival tumor tissue submitted as a baseline specimen must have been collected within 3 months prior to patient registration, and the patient must not have received any intervening cancer therapy since collection of the specimen. Archival tissue must be collected and processed according to SOP340507 (https://dctd.cancer.gov/ResearchResources/biomarkers/docs/par/SOP340507_Biopsy_Frozen.pdf), including flash-freezing in liquid nitrogen, minimal cold ischemia time (< 5 minutes), and shipment on dry ice.

Please send an email to FNLCR PD Specimen Central Receiving ([contact]) to advise that archival tissue is being prepared for shipment. State “Protocol Name PD Specimens Ready for Shipment” in the subject line. If needed, FNLCR PD Central Receiving can be contacted directly at [contact] or [contact].

9.3 Exploratory Genomic Analyses

As of **Amendment R** (5/12/2018), the MoCha laboratory will investigate the occurrence of tumor genomic alterations potentially associated with sensitivity and/or the development of resistance to TRC102 and temozolomide, such as the status of mismatch repair genes or the development of increased mutational load and neoantigen production. Whole exome (WES) and whole transcriptome (RNASeq) genomic analysis of tumor samples collected before and during treatment and upon progression will be performed and compared with data from germline tissue to identify somatic variants, which will be used to determine tumor mutational load and identify neoantigens.

9.3.1 Tumor Genomic Analyses

Tumor biopsies will be collected and processed as detailed in [Section 9.2.3.3](#).

9.3.1.1 Baseline and Cycle 1, Day 4/5 Biopsies

Paired tumor biopsy tissues collected at baseline and after treatment on cycle 1, day 4 or 5 will be used for exploratory targeted (OCAv3) and WES analyses only if there is sufficient tissue remaining after PD biomarker analyses have been completed ([Figure 4](#)). Tissue availability will be tracked in real time using Labmatrix. Although the MoCha Laboratory is CLIA-certified, these sequencing studies will not be done per CLIA specifications as these data will not be returned to the patients or used for clinical decision making.

9.3.1.2 Restaging Follow-Up and Progression Biopsies

Tumor tissue collected at the (optional) restaging follow-up or progression biopsy will be analyzed by the CLIA-certified OCAv3 assay and results will be returned to patients in the form of the Oncomine report. If additional tumor tissue is available after the OCAv3 analysis, exploratory, non-CLIA certified genomic analyses such as WES may be conducted but the results will not be returned to patients or used for clinical decision making ([Figure 4](#)). *Note: Per the discretion of the PI, restaging follow-up or progression biopsies may be used for other analyses, including analyses carried out as a part of other DTC clinical trials, providing that the tissue is collected per SOP for those analyses.*

9.3.2 Germline Genomic Analysis

One whole blood sample (10-mL Streck tube) will be collected before drug administration on cycle 1 day 1 (or another time while the patient is on study) and mononuclear cells isolated for nucleic acid extraction and exploratory WES and RNAseq to compare somatic variant calls, mutational load, MMR inactivation, and other potential markers of drug sensitivity or resistance to the tumor biopsy specimen, the results of which will not be returned to patients ([Figure 4](#)).

Blood specimens for germline genomic analysis will be shipped at ambient temperature to:

ATTN: [name]/[name]
MoCha Histology Lab
Frederick National Laboratory for Cancer Research
Leidos Biomedical Research, Inc.
[name]
[name]
[name]

Shipment Notification:
[contact]

Samples should be labeled with only the unique patient ID. **Do NOT include patient identifiers (e.g., medical record number, patient name, or initials) with the samples.**

Fig. 4. Summary of Planned Tumor and Germline Genomic Analyses:

Protocol	Sample Type	Collection Point	
TRC102			
TMZ			
	Tumor Biopsy:	↑ Baseline ↑ C1D4/5	
	Blood Sample:	↑ Baseline (or collected later for germline sequencing)	
		↑ Progression or Restaging Follow-up	
	Baseline and C1D4/5 Tumor Biopsies	Progression or Restaging Follow-up Biopsy	Blood Sample for Germline Sequencing
Collection Information	All biopsy tissues flash frozen	All biopsy tissues flash frozen	1 Streck tube
First Priority Assay(s)	PD assays	CLIA OCAv3 assay > non-CLIA WES and RNAseq	WES and RNAseq
Second Priority Assay(s)	WES and RNAseq	PD assays	
Reporting to Patients	None	Oncomine report from OCAv3 assay	Incidental findings only

9.3.3 Privacy Considerations

As patient clinical response data (both for this study and, potentially, after a patient is off-study) will be required for comparison to sequencing results, de-identifying the samples is not feasible. A Certificate of Confidentiality has been obtained to help protect the privacy of all study participants. The informed consent document for this protocol after **Amendment R** (5/12/2018) contains language informing patients about the performance of genetic studies, and patients will have the option to choose whether they wish to take part in these studies.

9.3.4 Management of Results and Genetic Counseling

Whole-exome sequencing (WES) of tumor and blood performed for research purposes can detect non-ambiguous germline variants, which may raise health and privacy implications for the patient and his or her family. WES will not be validated for clinical use, and no clinical decisions can be made based on its results.

The results of the CLIA-certified OCAv3 targeted sequencing assay on restaging follow-up or progression tumor biopsy tissue at MoCha (CLIA certification #21D2097127) will be returned to patients in the Oncomine report.

9.4 Sample Collection and Processing

Biospecimens will be collected and processed using validated SOPs that will ensure both specimen quality and patient confidentiality pursuant to informed consent provisions. Information about each specimen (e.g., blood, tumor biopsy, circulating tumor cells, per specific protocol) will be recorded on a PK/PD collection worksheet included in [Appendix D](#).

Using a computerized inventory system and a backup hardcopy process, all specimen collection and processing steps will be documented and the specific location of each specimen will be tracked. Each new specimen collected will be assigned a unique barcode identifier that can be linked to the original specimen collected and other relevant information within the inventory system. To ensure patient confidentiality, only containers used for the initial specimen collections will be labeled with patient identifiers.

Only the barcode identifier will be applied to all subsequent specimen containers. When specimens are processed and aliquoted, no patient information will be included on the new containers. Original specimen containers will be discarded. Only barcode-labeled specimens without patient identifiers will be shipped for analysis and/or storage.

Specimen labels will indicate: CTEP protocol number, unique patient accession number, 3-digit sample number (see list below), collection time, and total volume collected, as appropriate. Samples from sets of at least three patients will be grouped for scientific analysis.

Standardized 3-digit sample collection numbers:

- 000 series: blood for germline WES
- 100 series: urine for PK
- 200 series: blood for PK
- 300 series: blood for PD
- 400 series: blood for circulating tumor cells (CTCs)
- 500 series: tumor biopsies

The inventory process contains other security provisions sufficient to safeguard patient privacy and confidentiality. Access to the inventory system and associated documents will be restricted to appropriate individuals. Requests to use specimens stored in the repository must be approved. The only patient information available in the inventory system will be the patient sex, diagnosis, and level of informed consent given. SOPs ensure that any changes in informed consent made by a patient and relayed to the PI will be reflected in the inventory system to ensure that specimens are destroyed as appropriate. All laboratory personnel will be trained to adhere to SOPs and will be monitored for high-quality performance.

Any new use of these samples will require prospective IRB review and approval. Access to these samples will only be granted following IRB approval of an additional protocol, granting the rights to use the material.

If at any time, a patient withdraws from the study and does not wish for their existing samples to be utilized, the individual must provide a written request. Following receipt of this request, the samples will be destroyed (or returned to the patient, if so requested), and reported as such to the IRB. Any samples lost (in transit or by a researcher) or destroyed due to unknown sample integrity (i.e., broken freezer allows for extensive sample thawing, etc.) will be reported as such to the IRB.

9.4.1 Human Data Sharing Plan

What data will be shared?

We will share human data generated in this research for future research as follows:

- X De-identified data in an NIH-funded or approved public repository
- X Identified data in BTRIS (automatic for activities in the Clinical Center)
- X De-identified or identified data with approved outside collaborators under appropriate agreements

How and where will the data be shared?

Data will be shared through:

- X An NIH-funded or approved public repository: clinicaltrials.gov
- X BTRIS (automatic for activities in the Clinical Center)
- X Approved outside collaborators under appropriate individual agreements
- X Publication and/or public presentations

When will the data be shared?

- X At the time of publication or shortly thereafter

10. STUDY CALENDAR

Baseline evaluations are to be conducted within 8 days prior to start of protocol therapy. Scans and x-rays must be done \leq 4 weeks prior to the start of therapy. In the event that the patient's condition is deteriorating, laboratory evaluations should be repeated within 48 hours prior to initiation of the next cycle of therapy. Start of next cycle may be delayed for up to 1 week to accommodate scheduling conflicts. History and physical examination and laboratory evaluations can be performed up to 1 week before the start of the next cycle.

	Pre-Study	C1 W1	C1 W2 ^k	C1 W3 ^k	C1 W4 ^k	C2 W1 ^k	C2 W3	C3 W1 ^k	C3 W3 ^k on	Off Treatment ^j
TRC102/TMZ ^a		X				X		X		
Informed consent	X									
Demographics	X									
Medical history	X					X		X		
Concurrent meds	X	X-----						X		
Physical exam ^b	X	X				X		X		X

Vital signs	X					X		X		X
Height	X									
Weight	X					X		X		X
Performance status	X					X		X		X
CBC w/diff, plts ^c	X		X	X		X		X		
Serum chemistry ^c	X		X	X		X		X		
Anemia ^l	X	X	X							
PT, INR, PTT ^d	X									
β-HCG ^e	X									
AE evaluation			X-----X							X
Tumor measurements	X		Tumor measurements are repeated every 2 cycles (3 cycles for patients on study more than 1 year). Documentation (radiologic) must be provided for patients removed from study for progressive disease.							
Tumor biopsy ^f	X	X								
PK blood ^g		X								
Circulating tumor cells ^h		X				X				X
ECG ⁱ	X									

a: TRC102 and TMZ will be administered once daily, days 1-5, in 28 day cycles.
b: Physical exam at the Clinical Center should be performed at the start of each cycle (up to 1 week before start of a new cycle). Start of the next cycle may be delayed for up to 1 week to accommodate scheduling conflicts.
c: Serum chemistry (albumin, total bilirubin, calcium, creatinine, phosphorus, magnesium, potassium, sodium, SGOT [AST], SGPT [ALT], LDH); CBC w/diff, platelets up to week 3 during cycle 1 (Phase I only), and during week 1 in cycle 2 and subsequent cycles (up to 1 week before start of a new cycle) (Phase I and II). If clinically indicated, labs may be obtained more frequently.
d. PT/INR, PTT as clinically indicated.
e: Serum pregnancy test (women of childbearing potential) within 8 days prior to enrollment and as clinically indicated.
f: Tumor biopsies (mandatory only in Phase I expansion cohort and Phase II where appropriate) will be performed in patients who have disease amenable to biopsy prior to treatment and 3-4 hours after the 5th dose of TRC102 on C1D5 (\pm 1 day in case of scheduling difficulties; day 4 or 5, 3-4 hrs after drug for patients on Phase II reflecting likely start day/weekend timing). One optional biopsy at progression or on day 1 (\pm 2 days) of the cycle following any restaging at which a 10-19% increase in tumor volume is observed (according to RECIST criteria) for patients who have been on study for at least 4 cycles may also be obtained.
g: Phase I only: PK samples (optional) will be performed at the following time points: C1D1: Pre-dose, at 1, 2, 3, 4, 8, 12, and 24 hours after the first dose in both the escalation and expansion phases; C1D5 pre-dose in the expansion phase only. Additional PK sampling will be optional (but encouraged).
h: Circulating tumor cells (optional) will be collected as described in [Section 9.2](#)
i: ECG will be performed at baseline for evaluation of QTc and as clinically indicated thereafter.
j: Off-study evaluation.
k: \pm 1 day in case of scheduling difficulties

[I: refer to [Appendix F](#)]

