5. TREATMENT PLAN

Phase I: This is an open-label Phase I trial evaluating the combination of oral TRC102 with oral TMZ, in 28-day cycles. The starting dose of TRC102 is based on the safety information from the trial of IV TRC102 combined with TMZ. The study will follow a 3+3 design: dose will be escalated in cohorts of 3 patients with the individual dose of TRC102 and TMZ increased in successive dose levels as outlined in the dose escalation table below. Once the MTD is established, up to 15 additional patients will be enrolled at the MTD (expansion phase) to further define the dose and evaluate PK and PD at this dose level.

Phase II: Patients with a body surface area (BSA) of $\geq 1.6 \text{ m}^2$ will be started on 125 mg TRC 102 and 150 mg/m² Temozolomide orally on days 1-5 of each 28-day cycle (DL6). Patients with a BSA of $< 1.6 \text{ m}^2$ will be started on 100 mg TRC 102 and 150 mg/m² Temozolomide orally on days 1-5 of each 28-day cycle (DL5). There will be no dose escalation for patients on the Phase II portion of the study; appropriate dose modifications are described in [Section 6](#). Up to 75 patients will be accrued to this part of the study.

History and physical examination can be done up to 8 days before start of a new cycle. Patients will be examined at baseline for the first cycle then at the start of every cycle for the remainder of the study (up to 3 days before start of a new cycle). The start of the next cycle may be delayed for up to 1 week to accommodate scheduling conflicts.

Labs (CBC with differential; serum chemistries) will be performed (+/- 2 days) as follows: every week up to week 3 for cycle 1. Starting with cycle 2, labs (CBC with differential; serum chemistries) will only be performed before the start of each cycle (laboratory evaluation may be performed up to 7 days prior to scheduled date to accommodate scheduling conflicts and patient convenience). If clinically indicated, labs may be obtained more frequently.

Blood for erythrocyte analysis (optional) will be collected on cycle 1 days 7, 14, and 21 (+/- 2 days) as described in [Appendix F](#).

CT scans will be performed at baseline, and repeat scans will be performed every 2 cycles (every 3 cycles for patients on study more than one year).

Phase I Dose Escalation Schedule (28-day cycle)		
Dose Level	TRC 102 orally	TMZ orally
Level -2	25 mg once daily D1-5	75 mg/m ² once daily D1-5
Level -1	25 mg once daily D1-5	100 mg/m ² once daily D1-5

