5.1 Agent Administration

Reported adverse events and potential risks are described in [Section 7](#). Appropriate dose modifications are described in [Section 6](#). No investigational or commercial agents or therapies other than those described below may be administered with the intent to treat the patient's malignancy.

TRC102 will be administered to patients as a capsule dosed according to the dose escalation table. TRC102 should be administered together with TMZ capsules. TRC102/TMZ should be administered either 1 hour before or 2 hours after a meal. Patients should drink an eight ounce glass of water following TRC102/TMZ administration. Antiemetic therapy may be administered prior to and/or following administration of TRC102/TMZ in patients who develop nausea and vomiting but not prophylactically. TRC102/TMZ capsules should not be opened or chewed. If capsules are accidentally opened or damaged, precautions should be taken to avoid inhalation or contact with the skin or mucous membranes.

The drugs will be administered in 28-day cycles (\pm 1 day for scheduling). A missed or vomited dose will not be replaced. The patients will be instructed to take the next scheduled dose at the regularly scheduled time. Patients will be asked to maintain a Study Medication Diary ([Appendix C](#)) and record each dose of medication. Patients will be given instructions for completing the medication diary and will be asked to return it to the clinic staff at the end of each cycle.

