5.2 Definition of Dose-Limiting Toxicity (Phase I only)

For MTD determination, DLTs will be defined as toxicities occurring within the first cycle of treatment. Patients who come off study for reasons other than drug-related toxicity (e.g., disease progression) prior to completion of more than 90% of dose of the first cycle will be replaced. Dose-limiting toxicity (DLT) is defined as an adverse event that occurs during the first cycle and is felt to be related (possibly, probably, or definitely) to administration of study drugs and fulfills one of the following criteria:

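### Section 5 and calendar footnote c disagree on weekly cycle 1 blood counts in Phase II; under footnote c the Section 6.1 hematologic triggers for the cycle 2 dose rest on clinically prompted labs

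*Combined protocol and SAP*

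**What the plan says.** Three places in the current protocol set the cycle 1 safety labs.

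- **Section 5 (Treatment Plan).** CBC with differential and chemistries are done "every week up to week 3 for cycle 1", within 2 days either way. The sentence follows paragraphs on both phases and names neither. From cycle 2, labs are drawn only before each cycle starts, and "laboratory evaluation may be performed up to 7 days prior to scheduled date".
- **Section 10 calendar grid.** The CBC row is marked at pre-study, cycle 1 weeks 2 and 3, and week 1 of cycles 2 and 3. It is not split by phase.
- **Section 10, footnote c.** It gives "CBC w/diff, platelets up to week 3 during cycle 1 (Phase I only"), "and during week 1 in cycle 2 and subsequent cycles", and labels the later labs as applying to both phases.

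Section 6.1 holds both drugs and restarts them at the lower dose level in three hematologic situations: a hemoglobin drop of at least 3.0 g/dL over one week that results in grade 3 anemia, grade 3-4 neutropenia, and grade 3-4 thrombocytopenia. These rules carry no phase limit, and the Phase II paragraph of Section 5 refers to Section 6 for dose modifications. By contrast, Section 5.2 is headed "Definition of Dose-Limiting Toxicity (Phase I only").

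**The concern.** Footnote c uses two different phase labels in one sentence, so it cannot be read as covering Phase II in cycle 1. Section 5 cannot be read as excluding Phase II. A site can comply with one and deviate from the other.

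The conflict matters because Section 6.1 needs counts to act on. Under footnote c the pre-cycle-2 count can show that hemoglobin has fallen since baseline but not how fast. It cannot show a neutrophil or platelet nadir that has already recovered. A patient who met a reduction rule in cycle 1 could therefore start cycle 2 at the full dose.

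The toxicity is one the trial already knows. Section 2.5 names hemolytic anemia as the dose-limiting toxicity, with the MTD exceeded at dose level 8; Phase II uses levels 6 and 5. Section 3.1.7 admits patients with hemoglobin of 10 g/dL, and a 3.0 g/dL fall from there gives 10 - 3.0 = 7.0 g/dL, below the 8 g/dL at which Section 5.3.4 recommends transfusion.

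**Working it through.** The plan states no interval of its own, so there is no figure to reproduce. The check is date arithmetic, counting from cycle 1 day 1 as day 0.

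**Inputs**
- Baseline: "Baseline evaluations are to be conducted within 8 days prior to start of protocol therapy" (Section 10), so day -8 to day 0.
- Cycle length: "The drugs will be administered in 28-day cycles" (Section 5.1), with a window of 1 day either way. Cycle 2 starts on day 28 nominally.
- Pre-cycle-2 labs: up to 7 days early (Section 5 and footnote c), so day 21 to day 28.
- Delay: "Start of next cycle may be delayed for up to 1 week to accommodate scheduling conflicts" (Section 10).
- Dosing on days 1-5; the fifth dose is on day index 4.

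**Phase II, footnote c followed: baseline to next scheduled CBC**
- Shortest, undelayed: 21 - 0 = 21 days.
- Longest, undelayed: 28 - (-8) = 36 days.
- With the 1-week scheduling delay: 35 + 8 = 43 days.
- With the delay and the extra day of the cycle window: 36 + 8 = 44 days. Using the window the other way shortens the minimum to 20.

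**Fifth dose to first scheduled CBC, undelayed**
- 21 - 4 = 17 to 28 - 4 = 24 days. With the 1-week delay, up to 35 - 4 = 31.

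Every interval is well beyond the 7 days in the hemoglobin rule.

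**Phase II, Section 5 followed**
- A week 2 draw (study days 8 to 14, day index 7 to 13) comes 7 - 4 = 3 to 13 - 4 = 9 days after the fifth dose, before the 2-day window.
- Consecutive weekly draws, each movable by 2 days, are 7 - 4 = 3 to 7 + 4 = 11 days apart. The rule becomes assessable from scheduled labs, though an exact 7-day pair is not guaranteed.

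**Cycle 2 onward, either text**
- One pre-cycle CBC per cycle, 28 - 7 = 21 to 28 + 7 = 35 days apart when undelayed. The conflict is confined to cycle 1.

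**Cost of the weekly labs in Phase II**
- Two draws (grid, weeks 2 and 3) to three (Section 5), at the ceiling of 75 patients: 2 x 75 = 150 to 3 x 75 = 225 draws.

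**The case against.** The strongest reply is that footnote c may be deliberate. DLTs are assessed in Phase I only, weekly cycle 1 counts serve that purpose, and the paired phase labels look like a choice. That is plausible, and it is why the documents by themselves require only that the two sections agree. It does not settle how Section 6.1 works in Phase II, where it still applies.

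Second, the drugs are given on days 1-5 only, so a count in week 2 or 3 changes no cycle 1 dose. This stands. What is at stake is the cycle 2 dose level and supportive care.

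Third, there are other safeguards: labs when clinically indicated, repeat labs within 48 hours of the next cycle in a deteriorating patient, the Section 6 recovery criteria before restarting, transfusion guidance below 8 g/dL, and reporting of transfusion needs in the first 3 cycles (Section 7.2.4). These reduce the risk. None schedules a Phase II count in cycle 1, and the recovery criteria can delay a cycle but do not reveal a nadir that has resolved. Appendix F once offered optional CBCs on days 7, 14 and 21, but its header says that analysis ended with Amendment R.

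Fourth, the protocol already relies on prompted labs for the one-week rule from cycle 2. That is also true, and it limits what a cycle 1 fix can achieve.

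A reader might also infer a gap of up to 50 days by placing the cycle 2 labs on day 7 of that cycle (day index 34, plus 7 for delay and 1 for the window, plus 8 for baseline). The documents do not support this. Section 5 places those labs before the cycle starts, and the Section 6 recovery criteria need a count before dosing.

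**Conclusion.** The inconsistency is certain: two current texts give different cycle 1 lab schedules for Phase II, with no rule of precedence. Its consequence is conditional. Only where footnote c is followed is there no scheduled CBC for 21 to 36 days (up to 43 or 44 with permitted delays), with the first scheduled count 17 to 24 days after the fifth dose in an undelayed cycle. The Section 6.1 hematologic triggers then rest on clinically prompted labs in that cycle.

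A reader might infer that Phase II patients go unmonitored, or that the trial's conclusions are at risk. Neither follows. A site following Section 5 has no such gap, prompted labs are allowed throughout, and no sample size, error rate or Phase I DLT assessment is touched. Nor can the number of patients affected be judged: text under Current Protocol Status in Section 2.3 was removed from the copy reviewed, so nothing is concluded here about how often such hemoglobin falls occurred at dose levels 5 and 6.

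The intervals assume pre-cycle labs are drawn on or before day 1 of the cycle and that baseline is counted from the start of therapy. Section 3.4.4 counts it from enrollment, which could lengthen the gap.

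**What to change.** Make the two sections agree. The better option is to delete the Phase I restriction from footnote c, so that the weekly cycle 1 labs in Section 5 apply to Phase II as well. This matches the calendar grid as it stands. It costs one deletion and two to three routine draws per Phase II patient, 150 to 225 in total at 75 patients.

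If the sponsor does intend weekly labs for Phase I only, Section 5 and the grid should say so. The one-week hemoglobin trigger in Section 6.1 should then be restated so that it can be assessed from the Phase II labs, for example grade 3 anemia with a fall of at least 3.0 g/dL from the last count. This avoids the draws but leaves a recovered neutrophil or platelet nadir undetected unless a lab is prompted.

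The preferred change closes the gap for cycle 1 only. From cycle 2 both texts still schedule one CBC per cycle.
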